10.3. Populations for Analysis

Safety Population: All participants who receive at least one dose of study drug will be included in the safety population.

Pharmacokinetic Population: The PK population will consist of all participants who receive any amount of study drug and have at least one measured concentration at a scheduled PK time point after the start of dosing.

10.4. Data Analysis

Data will be presented by maximum dose level.

A TEAE, defined as an event that occurs on or after Day 1 of study drug or the worsening of a pre-existing condition on or after Day 1 of study drug, will be classified according to the Medical Dictionary for Regulatory Activities (MedDRA). The incidence of TEAEs and relatedness to study drug, as assessed by the Investigator, will be summarized descriptively by maximum dose level tolerated.

Clinical laboratory tests, ECGs, and vital signs over time will be summarized by maximum dose level tolerated using descriptive statistics. Change from baseline in ECG intervals will be evaluated using descriptive statistics. If an effect on mean change from baseline in QTc interval exceeding 10 msec is observed, concentration-QTc analysis may be explored. Results from the diagnostic interpretation will be summarized by maximum dose tolerated.

An Hb responder endpoint, defined as an increase in Hb of > 1 g/dL compared to Baseline, will be summarized. Additionally, change from baseline in hemoglobin and clinical measures of hemolysis (unconjugated bilirubin, % reticulocyte, absolute reticulocyte, and LDH) will be summarized by maximum dose level tolerated using descriptive statistics.

The incidence of VOCs will be summarized by maximum dose tolerated.

The CGI-C and PGI-C will be summarized by maximum dose level tolerated.

Population PK analysis using nonlinear mixed-effect modeling will be performed to characterize voxelotor PK in plasma, and whole blood.

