2.1. Primary Objective

- To evaluate the tolerability and safety of voxelotor at daily doses of > 1500 mg (2000 mg to 3000 mg) in participants with SCD

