3.2. Study Design

This is an open-label, sequential period, within-participant dose escalation study. Up to 40 participants with SCD (HbSS or HbSB⁰) who are 18 to $<$ 60 years of age, inclusive, will be enrolled.

Study participants will undergo up to four periods of voxelotor administration at progressively higher dose levels from 1500 mg until either a MTD or 3000 mg daily dose is reached, whichever occurs first ([Figure 2](#)):

- Period 1: 1500 mg per day: 1500 mg once daily (3×500 mg tablets) for 3 weeks (± 3 days)
- Period 2: 2000 mg per day: 1000 mg (2×500 mg) BID for 3 weeks (± 3 days)
- Period 3: 2500 mg per day: 1500 mg (3×500 mg) in morning and 1000 mg (2×500 mg) in evening daily for 3 weeks (± 3 days)
- Period 4: 3000 mg per day: 1500 mg (3×500 mg) BID for 3 weeks (± 3 days)
- Observation Period: MTD or 3000 mg daily for 24 weeks
- Safety Follow-up Period: from day of last dose to 28 days postdose.

[figure not shown]
If at any time a dose level $>$ 1500 mg is not tolerated by a participant in the dose escalation period, the dose may be reduced to a previous level for the participant, which will then be administered for 24 additional consecutive weeks as an observation period. Dose modifications are allowed during the observation period in consultation with the Sponsor's Medical Monitor ([Appendix C](#)).

If 1500 mg daily is the MTD for a participant, then the participant may enter the observation period and continue to receive 1500 mg, for up to 24 weeks or until they are able to roll over into the open-label extension or receive commercial voxelotor, where available. If the participant discontinues early from the study, the participant will undergo an End of Study (EOS) visit approximately 28 days after the last dose and will not be eligible for the open-label extension study.

The safety of study participants will be closely monitored by the study team. In addition, a Safety Monitoring Committee (SMC) will review safety, tolerability, and available PK and PD data at regular intervals (Section [3.4](#)). Blood draws for PK and PD (including Hb and hemolysis markers), routine chemistry and hematology laboratory tests, and 12-lead ECGs in triplicate will be obtained periodically, as listed in the Schedule of Assessments ([Appendix A](#), [Appendix B](#)).

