3.7.3. Early Discontinuation of Individual Participants

3.7.3.1. Individual Dose-limiting Toxicity Definition: Dose Escalation Period

Criteria for individual dose-limiting toxicity at doses beyond 1500 mg/day include, but are not limited to, the following:

- Any AE Grade ≥ 3 not clearly resulting from the underlying disease and deemed by the Investigator and/or Medical Monitor to be related to study drug.
- Worsening of an ongoing, treatment-related AE by ≥ 1 grade as per Investigator assessment
- Grade 3 nausea, vomiting, or diarrhea (deemed related to study drug) requiring hospitalization and/or intravenous fluids and parenteral tube feeding, total parenteral nutrition
- Study drug-related SAE

If any of these criteria is met, the Investigator should consider temporary dose reduction and/or study drug discontinuation for the individual participant after discussing with the Sponsor. If a subject discontinues early due to AEs, the subject will not be eligible for the open-label extension study.

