9.2. Adverse Event Reporting

9.2.1. General

All AEs will be recorded from the time the study participant signs the ICF until 28 days after the last dose of study drug. After this period, the Investigator should report only SAEs that are assessed as related to study drug until the EOS visit occurs. All SAEs must be reported within 24 hours of SAE awareness on the AE CRF via the electronic data capture (EDC) system. The Investigator is responsible for evaluating all AEs, obtaining supporting documents, and ensuring documentation of the event is complete. Details of each reported AE must include at minimum severity, relationship to study drug, duration and outcome. All (both serious and nonserious) AEs must be followed until they are resolved or stabilized, or until reasonable attempts to determine resolution of the event are exhausted.

Any participant who experiences an AE may be discontinued from study drug at any time at the discretion of the Investigator. The Sponsor and the CRO's Medical Monitors must be notified of the study participant's discontinuation.

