9.2.3. Abnormal Laboratory Values

Only clinically significant laboratory abnormalities will be recorded on the AE CRF (eg, abnormalities that have clinical sequelae, require study drug dose modification, discontinuation of study drug, more frequent follow-up assessments, further diagnostic investigation). If the clinically significant laboratory abnormality is a sign of a disease or syndrome (eg, ALP and bilirubin above the ULN associated with cholecystitis), only the diagnosis (eg, cholecystitis) needs to be recorded on the CRF.

If the clinically significant laboratory abnormality is not a sign of a disease or syndrome, the abnormality itself should be recorded on the CRF. If the laboratory abnormality can be characterized by a precise clinical term, the clinical term should be recorded. For example, an elevated serum potassium level of 7.0 mEq/L should be recorded as “hyperkalemia.”

Observations of the same clinically significant laboratory abnormality from visit to visit should not be repeatedly recorded on the AE CRF, unless their severity, seriousness, or etiology changes.

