9.2.4. Pre-existing Medical Conditions

A pre-existing medical condition is one that is present at the start of the study. Such conditions should be recorded on the Medical History and Baseline Conditions CRF.

If a pre-existing medical condition increases in frequency or severity, or if the character of the condition worsens during the study, the condition should be recorded as an AE or SAE. When recording such events on the AE CRF, it is important to convey the concept that the pre-existing condition has changed by including applicable descriptors (eg, “more frequent headaches”).

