10. DATA ANALYSIS AND STATISTICAL PLANS

10.1. Endpoints

10.1.1. Primary Endpoint

The primary endpoints are:

- TEAEs and SAEs

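### The planned TEAE summary cannot show the grade increase, or its dose, when a non-serious, non-laboratory AE that began at 1500 mg worsens at a higher dose

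*Combined protocol and SAP*

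**What the plan says.** Section 10.1.1 names "TEAEs and SAEs" as the primary endpoints. The primary objective in Section 2.1 concerns doses of 2000 to 3000 mg/day, and Section 1.5.1 adds that results are to be compared with the 1500 mg dose. On design, Section 3.2 states: "This is an open-label, sequential period, within-participant dose escalation study". Everyone begins at 1500 mg/day and may then move to 2000, 2500 and 3000 mg/day.

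Section 10.4 defines a TEAE as an event from Day 1 onward "or the worsening of a pre-existing condition on or after Day 1 of study drug". Section 9.2.4 fixes the key term: "A pre-existing medical condition is one that is present at the start of the study". The general AE definition in Section 9.1.1 ties its own worsening clause to pre-existing conditions in the same way.

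On recording, Section 9.2.1 says: "Details of each reported AE must include at minimum severity, relationship to study drug, duration and outcome". For laboratory abnormalities only, Section 9.2.3 says that repeat observations "should not be repeatedly recorded on the AE CRF, unless their severity, seriousness, or etiology changes".

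Among the individual dose-limiting criteria for doses beyond 1500 mg/day, Section 3.7.3.1 lists "Worsening of an ongoing, treatment-related AE by" one grade or more.

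For TEAEs, Section 10.4 plans incidence and relatedness, grouped by the highest dose each participant tolerated. It names no summary by grade, by dose at onset, by dose at worsening, or of dose-limiting toxicities.

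**The concern.** A TEAE definition that looks for worsening only against the state before treatment suits a trial in which each participant stays on one dose. Here the dose changes within the participant, and the state that matters for a higher dose is the state at the end of the dose below it. A mild AE that appears at 1500 mg and becomes moderate or severe at 2500 mg is direct evidence about 2500 mg.

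The protocol accepts this for managing the individual, because such a rise is a dose-limiting criterion. The analysis does not carry it through. Section 10.2 rests the assessment of an MTD on descriptive summaries of safety and PK data, so the TEAE summary has to be able to show what happened at each dose. Low-grade AEs at the starting dose are to be expected: Section 1.4 lists headache, diarrhea, abdominal pain, nausea, fatigue and rash among the common reactions at 1500 mg, and Section 1.5.1 describes treatment-related AEs as mostly Grade 1 or 2 gastrointestinal events.

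**Working it through.** There is no plan figure to reproduce. The study is descriptive, and the sample size has no assumed event rate behind it. The check is a reading of the rules, followed by worked cases.

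**Step 1. Does the worsening clause reach an on-treatment AE?** The clause in Section 10.4 needs a pre-existing condition. Section 9.2.4 makes that a condition present when the study starts. An AE that first appears in Period 1 is not one. It is a TEAE through the first half of the definition, because it began after Day 1, and its later rise in grade adds nothing further. Appendix A gives every period its own Day 1, so the reference day could be read in more than one way. Reading it as the start of each period would not help, because Section 9.2.4 still ties pre-existing to the start of the study.

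**Step 2. Is the rise recorded?** For laboratory AEs, yes: Section 9.2.3 calls for a new entry when severity changes. For other AEs, no rule is given. Section 9.2.1 requires severity and duration but does not say what to do when the grade changes.

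**Step 3. Does the planned summary show it?** Take three hypothetical participants, each with one related, non-serious, non-laboratory AE that starts at Grade 1 on 1500 mg.

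| Participant | Later course | Highest tolerated dose | Entry in the planned TEAE incidence |
|---|---|---|---|
| A | stays Grade 1 | 3000 mg | once, 3000 mg group |
| B | Grade 2 at 3000 mg, dose kept | 3000 mg | once, 3000 mg group |
| C | Grade 3 at 2500 mg, dose reduced | 2000 mg | once, 2000 mg group |

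A and B give the same entry, although B met a dose-limiting criterion. C appears under 2000 mg, which is neither the onset dose (1500 mg) nor the dose at worsening (2500 mg), and the step from Grade 1 to Grade 3 is not shown.

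**Step 4. What would recover it?** If only the TEAE definition is widened and the grouping is kept, C still counts once under 2000 mg. If grade increases are also dated and tabulated by current dose, C shows as Grade 1 at 1500 mg and Grade 3 at 2500 mg, and B shows a Grade 2 event at 3000 mg. Both the record and the table are needed.

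**Step 5. Size.** The count would need the proportion of participants with an AE still ongoing when they escalate and the proportion of those AEs that worsen. Neither is given. The figure of at least 10% in Section 1.4 is an incidence over treatment, not the share with an ongoing AE after three weeks. For scale only, one participant is 1/40 = 2.5% of the maximum enrollment, or 1/6 = 16.7% of the minimum of 6 sought at the study-level MTD.

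**The case against.** Four points can be made against the concern.

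First, a reader might infer that worsening at a higher dose is charged to 1500 mg and so makes the higher doses look safer. The documents do not support that. No planned table groups TEAEs by dose at onset, and in a participant who tolerates 3000 mg even the Period 1 events fall in the 3000 mg group. The defect is lost information, not a bias of known direction.

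Second, a reader might infer that such an AE must remain one record with one severity. No section says so. Section 9.2.1 sets a minimum content, Section 9 has ongoing AEs asked about at each visit, and Section 9.2.3 provides the opposite for laboratory AEs. The CRF may handle grade changes well, but it cannot be seen here. For other AEs the plan is silent, which leaves sites free to differ.

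Third, it would be too broad to say that the primary endpoint misses worsening altogether. The AE is counted as a TEAE, and worsening that becomes serious is an SAE and also counts. A dose-limiting rise may lead to a lower dose, which moves the participant to another group. The SMC reviews all safety data.

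Fourth, any percentage put on the problem would rest on invented rates.

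All four stand and narrow the point. None of them puts a non-serious grade increase, or the dose at which it happened, into the planned summary.

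**Conclusion.** The concern holds in limited form. For non-serious, non-laboratory AEs that begin at 1500 mg, the planned TEAE summary cannot show a later grade increase or its dose, while Section 3.7.3.1 treats a related increase of at least one grade above 1500 mg/day as dose-limiting. Two features act together: a worsening clause limited to conditions present at study start, and a summary of incidence and relatedness by highest tolerated dose only. The second is the larger cause. The missing recording rule means that the information may not be recoverable afterwards.

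The number of participants affected cannot be computed from the documents. The conclusion assumes that Section 10.4 lists what is planned and that no CRF instruction outside these documents supplies the missing rule. The change should be made, because the primary objective is about the higher doses and the cost is small.

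**What to change.** - **Section 9.2.1:** extend the approach of Section 9.2.3 to all AEs. Each increase in grade becomes a new record with its own start date and the daily dose on that date, linked to the parent event.
- **Section 10.4, definition:** for each dose level, a TEAE is an event that starts, or rises above its grade at the first dose of that level, while the participant is on that level.
- **Section 10.4, tables:** in addition to the summary by highest tolerated dose, tabulate TEAE incidence and worst grade by dose at onset or worsening, with the participants treated at that level as the denominator. Time on a level ranges from about 3 weeks in escalation to 24 weeks in the Observation Period, so show the two phases separately or report time on each level.
- **Section 10.4, wording:** state that the Day 1 in the TEAE definition is the first dose in Period 1.

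The cost is one CRF completion rule, a few sentences, more AE records per participant and one additional set of tables. The recording rule needs to apply prospectively, since dates of grade changes may be hard to reconstruct later.

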Statistical Methods (continued)	
Secondary Endpoints
 
• Change in Hb and clinical measures of hemolysis (unconjugated bilirubin, % reticulocyte, absolute reticulocyte, and lactate dehydrogenase [LDH]) from Baseline• Proportion of participants with an Hb increase > 1 g/dL compared to Baseline• Incidence rate of VOCs 
Exploratory Endpoints
 
• P50 and P20 at 8 hours and 24 hours postdose• PK of voxelotor as assessed by population PK analysis using nonlinear mixed-effect modeling• % Hb occupancy at 8 hours and 24 hours postdose• CGI-C• PGI-C 
Sample Size
 
As this is an exploratory study to provide descriptive information on the tolerability, safety and efficacy of voxelotor at dose levels > 1500 mg daily, the sample size chosen was based on previous experience in exploratory studies to support the assessment of a MTD based on descriptive summaries of safety and PK data. The sample size of up to 40 participants takes into account the differential tolerance in participants, some potentially tolerating 3000 mg daily, while others only tolerating lower dose levels. An effort will be made to enroll a number of subjects sufficient to ensure that at least 6 participants are treated at the study level MTD.
 
Populations for Analysis
 
Safety Population: All participants who receive at least one dose of study drug will be included in the safety population.
 
PK Population: The PK population will consist of all participants who receive any amount of study drug and have at least one measured concentration at a scheduled PK time point after the start of dosing.
 
Analyses
 
TEAEs, defined as events that occur on or after Day 1 of study drug or the worsening of a pre-existing condition on or after Day 1 of study drug, will be classified according to the Medical Dictionary for Regulatory Activities (MedDRA). The incidence of TEAEs and relatedness to study drug, as assessed by the Investigator, will be summarized descriptively by maximum dose level tolerated.
 
Clinical laboratory tests, ECGs, and vital signs over time will be summarized by maximum dose level tolerated using descriptive statistics.
 
An Hb responder endpoint, defined as an increase in Hb of > 1 g/dL compared to Baseline, will be summarized. Additionally, change from baseline in Hb and clinical measures of hemolysis (unconjugated bilirubin, % reticulocyte, absolute reticulocyte, and LDH) will be summarized by maximum dose level tolerated using descriptive statistics.
 
The incidence of VOCs will be summarized by maximum dose tolerated.

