1.5.1. Study Rationale

In the pivotal Phase 3 Study GBT440-031, voxelotor was shown to have a dose-dependent (1500 mg > 900 mg orally daily), and clinically meaningful increase in Hb, as well as concurrent reductions in clinical measures of hemolysis. Study GBT440-029, is designed to assess tolerability, safety, and PD of voxelotor dose levels higher than 1500 mg daily (the maximum dose in the pivotal Phase 3 study) and to compare these results to the 1500 mg dose. The rationale for this study is based on an exposure-response analysis from the pivotal Study GBT440-031, which showed a linear relationship between whole blood voxelotor and %Hb occupancy and efficacy as measured by improvement in Hb (see Figure 1 below) and hemolysis markers. The 1500 mg dose led to a mean Hb occupancy of 29% and led to a mean Hb increase of 1.1 g/dL. At 3000 mg of voxelotor, assuming a linear relationship, the mean Hb occupancy is projected to be 49.3% with a Hb increase of 2.04 g/dL. Furthermore, no dose level has been associated with exposure-related concerning safety signals, and a maximum tolerated dose (MTD) has not been defined. Treatment-related AEs were mostly grade 1/grade 2 gastrointestinal events. Given the predicted improved efficacy of higher doses, and lack of dose-limiting safety concerns, this study will investigate the potential for a greater benefit/risk for higher doses in patients with SCD.

In this study, baseline response will be characterized in participants receiving a 3-week treatment regimen with voxelotor 1500 mg and compared, within and across participants, to the response with the highest dose level tolerated at steady state. Dose escalation will be done in 3-week increments to assess tolerability at the escalated dose.

Figure 1: Relationships Between Change from Baseline in Hemoglobin at Week 24 and Percent Hemoglobin Occupancy

pkpd-wk24-hgb-20190508.pdf

C_{min} , minimum plasma concentration at steady state; CFB, change from baseline; Hb, hemoglobin.

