3.4. Safety Monitoring Committee

The SMC will closely monitor the safety of the study participants throughout the duration of study. The SMC will review the totality of safety, tolerability, and available PK and PD data to monitor safety.

The SMC will be composed of the Principal Investigator or designee and Sponsor representatives, including the Study Director/Medical Monitor, Clinician with disease expertise, Biostatistician, and Safety Scientist. Details of the scope, responsibilities, and frequency of the SMC will be provided in the SMC Charter.

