3.7.2. Cohort Dose Escalation Stopping Rules

- If ≥ 3 participants at a given dose level experience similar and related serious adverse events (SAEs), dose escalation will be paused until the SMC assesses the safety data and makes a recommendation.
- Progression to the next higher dose level can also be stopped if the SMC recommends discontinuation of dose escalation based on the totality of safety data.

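### The primary-endpoint table groups adverse events by the dose finally tolerated, a grouping set largely by adverse events. It gives no event rates by dose and can reverse 2500 and 3000 mg for dose-limiting events.

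*Combined protocol and SAP*

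**What the plan says.** The primary endpoints are TEAEs and SAEs (Section 10.1.1). The primary objective in Section 2.1 is "To evaluate the tolerability and safety of voxelotor at daily doses of > 1500 mg", specified there as 2000 to 3000 mg.

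Section 10.4 counts as a TEAE any event from Day 1 onward, whatever dose was being taken, and gives one grouping: "The incidence of TEAEs and relatedness to study drug, as assessed by the Investigator, will be summarized descriptively by maximum dose level tolerated". The synopsis repeats that TEAEs "will be summarized descriptively by maximum dose level tolerated". Section 10.4 also opens by saying that data are presented by maximum dose level, without the word tolerated.

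On how the group arises, Section 3.2 says that if a dose above 1500 mg is not tolerated, "the dose may be reduced to a previous level for the participant, which will then be administered for 24 additional consecutive weeks". The final dose is then held: "Observation Period: MTD or 3000 mg daily for 24 weeks". All four dose-limiting criteria listed in Section 3.7.3.1 are adverse events, though the list is not exhaustive.

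Elsewhere the protocol reasons by the dose being taken. Section 1.5.1 says "Dose escalation will be done in 3-week increments to assess tolerability at the escalated dose", and the pause rule in Section 3.7.2 counts participants who "at a given dose level experience similar and related serious adverse events".

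**The concern.** The column variable depends on the outcome being tabulated. A participant with a dose-limiting event on 3000 mg who is permanently reduced appears under 2500 mg. One whose event was on 2000 mg appears under 1500 mg, outside the range named in the primary objective. Conversely, events on 1500 to 2500 mg in participants who go on to 3000 mg are filed under 3000 mg.

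The objective needs events that began on a dose, divided by participants who started that dose. No section plans TEAEs by dose at onset, by period, or per person-time at a dose. For dose-limiting events, a reader could conclude that 2500 mg is tolerated far worse than 3000 mg when the truth is the reverse.

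Three smaller gaps go with this:

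- Section 10.4 alternates between maximum dose level and maximum dose level tolerated.
- It gives no column for a participant who stops early or does not tolerate 1500 mg.
- VOCs largely do not set the group (Sections 3.7.3.1 and 9.2.5), but the table pools doses with unequal exposure. Section 10.4 gives no denominator, although the endpoint in Section 10.1.2 is an incidence rate.

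**Working it through.** The plan has no figure to reproduce: Section 10.2 bases up to 40 participants on previous experience and gives no event rate. All rates below are assumptions. N = 40, and only escalation-period events are modelled.

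**Exposure (Section 3.2).** A participant who completes at 3000 mg has 4 × 3 + 24 = 36 nominal weeks. Of these, 3 × 3 = 9 weeks (25%) are at lower doses and 27 are at 3000 mg.

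**Limiting case.** True dose-limiting rates are 10/20/30% at 2000/2500/3000 mg, every event leads to lasting reduction by one level, and nobody leaves for other reasons. Starters are 40, then 40 × 0.9 = 36, then 36 × 0.8 = 28.8. Events are 4.0, 7.2 and 8.6.

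| Dose | By dose at onset | Planned column |
|---|---|---|
| 1500 mg | not modelled | 4.0/4.0 = 100% |
| 2000 mg | 4.0/40 = 10% | 7.2/7.2 = 100% |
| 2500 mg | 7.2/36 = 20% | 8.6/8.6 = 100% |
| 3000 mg | 8.6/28.8 = 30% | 0/20.2 = 0% |

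This is an extreme, not the expected result.

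**Relaxed model.** At level k, n_k participants start and a share p_k have a dose-limiting event. A share r of these return to the original dose and continue; the rest are filed one level down. Of those without an event at that level, a share d leave for non-AE reasons. Starters at the next level are n_k × [r·p_k + (1 − p_k)(1 − d)]. A participant counts in a column if an event occurred at any level. The plan does not say where event-free exits are filed, so I used two conventions: (A) at the dose being taken, (B) one level lower.

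Worked example under A, with p = 10/20/30%, r = 0.6, d = 0.10:

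- Starters: 40; 40 × (0.06 + 0.81) = 34.8; 34.8 × (0.12 + 0.72) = 29.23.
- 2500 mg column size: exits 34.8 × 0.8 × 0.1 = 2.78, plus reductions from 3000 mg 29.23 × 0.3 × 0.4 = 3.51, total 6.29. With an event: 3.51 plus 0.19 exits with an earlier event (40 × 0.1 × 0.6 × 0.8 × 0.1), so 3.70/6.29 = 59%.
- 3000 mg column: size 29.23 − 3.51 = 25.7, with 9.4 having had an event, so 37%.

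Percent with a dose-limiting event in the 1500/2000/2500/3000 mg columns, true rates 10/20/30%:

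| Return r | Exit d | Convention A | Convention B |
|---|---|---|---|
| 30% | 5% | 100/73/82/21 | 61/79/87/21 |
| 60% | 5% | 100/62/74/36 | 47/69/82/36 |
| 60% | 10% | 100/44/59/37 | 31/53/71/38 |

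**Grid.** Two rate sets (5/10/20% and 10/20/30%), r of 0/30/60% and d of 0/5/10% give 2 × 3 × 3 = 18 scenarios. The 2500 mg column exceeds the 3000 mg column in all 18, by 22.3 to 100 points under A and 32.1 to 100 under B. The assumed true rate at 2500 mg is always 10 points lower. That 3000 mg is the lowest of all columns is less robust: 18 of 18 under A and 16 of 18 under B, falling to 16 and 14 if Period 1 exits are added.

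**Reading the label as highest dose received.** In the limiting case the 3000 mg column becomes 8.6/28.8 = 30%, which is correct, but 2500 mg is 7.2/7.2 = 100%. Over the grid, 2500 mg still exceeds 3000 mg by 5.1 to 80 points.

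**Can the rates be recovered?** Take each column size over those not in a lower column. The limiting case gives 10/20/30%, which is correct. With r = 60% and d = 10% it gives 4.0/16.6/19.7% (A) or 13.0/16.0/19.0% (B), so recovery fails.

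**What dose at onset would report.** Limiting case rounded to whole participants, exact 95% intervals: 4/40 = 10% (2.8 to 23.7), 7/36 = 19% (8.2 to 36.0), 9/29 = 31% (15.3 to 50.8).

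**Need for a common window.** With a constant hazard h, the crude percentage over t weeks is 1 − exp(−h·t). At h = 0.01 per week it is 3.0% over 3 weeks and 23.7% over 27; at h = 0.02 it is 5.8% and 41.7%. Crude percentages by onset dose therefore mislead if a 3-week exposure is set against a 27-week one.

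**The case against.** **The study is exploratory and descriptive.** No test or decision rule hangs on this table. The committee's remit is wider: "The SMC will review the totality of safety, tolerability, and available PK and PD data to monitor safety". The pause rule already counts related SAEs by dose level, and Section 10.4 does not forbid further tables. This stands as far as it goes: the point concerns the reported primary-endpoint summary, not escalation decisions. But descriptive summaries are this study's main output, and Section 10.2 rests the MTD assessment on summaries of safety and PK data. Leaving the dose-at-onset table to be added later means choosing it after open-label data have been seen.

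**The reversal depends on the assumptions.** Reduction is discretionary (Section 3.7.3.1), Appendix C allows return to the original dose, and participants can leave without intolerance (Sections 3.7.3.2, 5.8.2, 5.8.3 and 8.17). Outside the grid, under convention A with 10/20/30%, the 2500 v 3000 mg columns are 46.9 v 47.2 (90% return, 5% exit), 36.2 v 45.4 (80%, 15%) and 32.7 v 48.0 (90%, 10%), so the order is right. On the highest-dose-received reading the order is right at 60% return and 15% exit (44.4 v 44.8). This stands, and limits the claim to *can* reverse. Even where the order is right, the columns are not the rates by dose.

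**Most TEAEs are not dose-limiting.** If 90% of participants had some other TEAE whatever their column, 82% v 21% would become 1 − 0.18 × 0.1 = 98% v 1 − 0.79 × 0.1 = 92%. This stands for an any-TEAE row; such events may even rise across columns. The reversal would appear in severe, related or term-level rows.

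**Small columns.** Several percentages rest on 1.6 to 7.5 expected participants, and a reader shown the denominators would be cautious. True, but caution does not supply the missing denominator.

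**Onset-dose tables are imperfect.** Dose is confounded with period, and starters at each level have passed the one before. This also stands, and should be stated beside the new table.

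**Conclusion.** The concern holds. As written, the only planned summary of the primary endpoint does not report events that began on a dose over participants who started that dose, which is what an objective about 2000 to 3000 mg requires. That conclusion follows from the text and needs no assumed rates.

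The size of the distortion does rest on assumed event, return and exit rates, on escalation-period events only, and on dose-limiting events only. Within those limits the 2500 mg column overstates relative to 3000 mg by 22 points or more throughout the grid. The reversal is possible and plausible, but not certain.

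**What to change.** Amend Section 10.4 and the matching synopsis text:

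1. Make the main summary of TEAEs, SAEs and VOCs by dose level being taken at onset. The denominator is participants who took at least one dose at that level, with events per person-time at that level. Compare crude percentages across doses only within a common window, the 3-week escalation period at each level, and report the observation period separately by dose and person-time. State how events during a hold or after the last dose are assigned. Note that late-onset events may be credited to the next dose, that dose is confounded with period, and that starters are selected for having passed the previous level. Define the VOC incidence rate with its person-time denominator.
2. Add the proportion with a Section 3.7.3.1 dose-limiting toxicity among those starting each level above 1500 mg in the escalation period, with exact 95% confidence intervals and the same note on selection.
3. Keep the maximum-tolerated-dose table as supportive. Use one label for the grouping, and state the column for participants who stop early, with or without an event, or who do not tolerate 1500 mg.

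The cost is wording, one dose-at-onset derivation and a few tables. Section 11.2 already collects adverse events and treatment administration. No dosing rule or study procedure changes.
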